11.5 Subject Compliance Monitoring

Compliance will be monitored by office visit documentation.

11.6 Prior and Concomitant Therapy

All history pertaining to prior and/or concomitant medical therapy will be collected at the time of study enrollment. See [**Section 8.3**](#) for details regarding which concomitant medications/therapies are permitted during the study.

11.7 Packaging

Atezolizumab, carboplatin and etoposide are considered non-Investigational Medicinal Products (NIMPs). Atezolizumab, carboplatin and etoposide will be used in the commercially available formulation. For information on the formulation, packaging, and handling of carboplatin and etoposide see the prescribing information for each drug.

11.8 Receiving, Storage, Dispensing and Return

11.8.1 Receipt of Drug Supplies

Atezolizumab, carboplatin and etoposide will be used in the commercially available formulation since they are NIMPs.

11.8.2 Storage

Storage conditions are described in the Manufacturer's Package Insert for atezolizumab, carboplatin and etoposide.

11.8.3 Dispensing of Study Drug

Regular study drug reconciliation will be performed to document drug administration. This reconciliation will be logged on the drug reconciliation form, and signed and dated by the study team.

**Columbia University Irving Medical Center
Herbert Irving Comprehensive Cancer Center
CUMC IRB – AAAT0174**

12 STUDY CALENDAR

		Every 3 week cycles (± 2 days)						
Procedure/Intervention ^a	Screening	Induction Phase				Maintenance Phase	Treatment Discontinuation Visit	Survival Follow up
	Days -28 to -1	C1D 1	C2D 1	C3D 1	C4D 1	CXD1	<30 days after last dose	Every 3 months
Informed Consent	X							
Tumor Biopsy ^b	X							
Liver metastasis biopsy ^c	X							
Clinical Assessments								
Medical and Cancer History	X							
Physical Examination	X	X	X	X	X	X	X	
ECOG performance status	X	X	X	X	X	X	X	
Vital signs	X	X	X	X	X	X	X	
12 Lead ECG	X							
Concomitant Medications	X	X	X	X	X	X	X	
Adverse Events ^d			X	X	X	X	X	
Survival Status ^e								X
Treatment								
Atezolizumab ^f		X	X	X	X	X		
Carboplatin ^g		X	X	X	X			
Etoposide ^g		X	X	X	X			
Liver-directed radiation ^h			X					
Tumor Assessments								
Optional tumor biopsy		At time of progression						
Brain MRI or CT head w/ contrast	X							
CT chest and abdomen w/ contrast ⁱ	X ^j				X	X ^k	X	X ^l
PET/CT (if applicable)	X							
Laboratory Assessments^m								
CBC	X	X	X	X	X	X	X	
Chemistry ⁿ	X	X	X	X	X	X	X	
PT/PTT	X							
TSH, free T3, free T4 ^o	X	X			X	X	X	
Urinalysis	X						X	
Serum beta-HCG ^p	X	X						
EBV, HIV, HCV, HBV serology ^q	X							
Research bloods ^r	X _{s,t}	X ^t	X ^t	X ^t	X ^t	X ^t	X ^t	

**Columbia University Irving Medical Center
Herbert Irving Comprehensive Cancer Center
CUMC IRB – AAAT0174**

1. Assessments should be performed prior to study drug infusion
2. Histologic confirmation of SCLC diagnosis
3. Liver biopsy must be obtained prior to pre-treatment for evaluation of exploratory biomarkers
4. All serious adverse events and adverse events of special interest, regardless of relationship to study drug, will be reported until 90 days after the last dose of study drug or initiation of new anti-cancer therapy, whichever occurs first. All other adverse events, regardless of relationship to study drug, will be reported until 30 days after the last dose of study drug or initiation of new anti-cancer therapy, whichever occurs first. After this period, the investigator should report any serious adverse events or adverse events of special interest believed to be related prior to study drug treatment.
5. Survival visits are to occur every 4 to 6 months from the date of the 6 month Follow-up visit. Survival follow-up information will be collected via telephone calls, patient medical records, and/or clinic visits. Study staff may use a public information source (e.g., county records), when permissible, to obtain information about survival status only.
6. For atezolizumab, the initial dose will be delivered over 60 (± 15) minutes. If the first infusion is well tolerated, all subsequent infusions may be delivered over 30 (± 10) minutes until loss of clinical benefit.
7. For carboplatin and etoposide, drug should be administered as described in [Section 11](#)
8. Liver directed radiation with three doses of 10Gy delivered on alternate days up to three liver lesions measuring no greater than 5 cm each should be started within 7 (+/-3) days of C2D1
9. CT scans (with oral/IV contrast unless contraindicated) or MRI scans of the chest and abdomen.
10. A CT scan of the pelvis is required at screening and as clinically indicated or as per local standard-of-care at subsequent response evaluations.
11. Perform every 6 weeks (± 7 days) (approximately every two cycles) for 12 months following Cycle 1, Day 1 and then every 9 weeks (± 7 days) thereafter, regardless of treatment delays, until radiographic disease progression, withdrawal of consent, death, or study termination by the Sponsor, whichever occurs first. Patients who continue treatment beyond radiographic disease progression per RECIST v1.1 will continue to undergo tumor assessments every 6 weeks (± 7 days) or sooner if symptomatic deterioration occurs. For these patients, tumor assessments should continue every 6 weeks (± 7 days), regardless of time on study, until study treatment is discontinued.
12. If the patient discontinued study treatment for any reason other than disease progression (e.g., toxicity), tumor assessments will continue at the same frequency as would have been followed if the patient had remained on study treatment until radiographic disease progression, withdrawal of consent, death, or study termination by the principal investigator, whichever occurs first, even if the patient starts another anti-cancer therapy after study treatment discontinuation, unless consent is withdrawn.
13. Laboratory assessments to be done within 2 days prior to study drug infusion.
14. Serum chemistries include Albumin, alkaline phosphatase, total bilirubin, bicarbonate, BUN, calcium, chloride, creatinine, glucose, LDH, phosphorus, potassium, total protein, SGOT [AST], SGPT [ALT], sodium, and magnesium.
15. Thyroid function testing (TSH, free T3, free T4) collected at Cycle 1, Day 1 and every fourth cycle thereafter.
16. Serum pregnancy test must be performed within 14 days prior to C1D1.
17. HBV DNA must be collected on or before Cycle 1, Day 1 in patients who have negative serology for hepatitis B surface antigen and positive serology for HBcAb. HCV RNA must be collected on

**Columbia University Irving Medical Center
Herbert Irving Comprehensive Cancer Center
CUMC IRB – AAAT0174**

or before Cycle 1, Day 1 in patients who test positive for anti-HCV. Screening EBV serology samples will be collected, but tests will be performed only if patients subsequently experience an acute inflammatory event such as systemic inflammatory response syndrome while receiving study treatment.

18. Research Blood Samples are not to be collected on days when treatment is being delayed or held.
19. At screening, research bloods will be drawn for a) germline sequencing as a companion to somatic tumor DNA sequencing , b) T-cell subsets, and c) HLA-typing (see **Laboratory Manual**)
20. PBMC isolation, serum and plasma (see **Laboratory Manual**)

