Important medical events are those that may not be immediately life threatening, but are clearly of major clinical significance. They may jeopardize the subject, and may require intervention to prevent one of the other serious outcomes noted above. For example, drug overdose or abuse, a seizure that did not result in in-patient hospitalization or intensive treatment of bronchospasm in an emergency department would typically be considered serious.

All adverse events that do not meet any of the criteria for serious events should be regarded as non-serious adverse events.

Serious adverse events are required to be reported by the investigator to the Sponsor immediately (i.e., no more than 24 hours after learning of the event; see Section 10.4 for reporting instructions).

Unanticipated Problem:

An unanticipated problem is any incident, experience or outcome involving risks to subjects or others in any human subjects research that meets all of the following criteria:

- Unexpected (in terms of nature, severity or frequency) given (a) the research procedures that are described in the IRB-approved protocol and informed consent document, and (b) the characteristics of the subject population being studied;
- Related or possibly related to participation in such research (e.g., there is a reasonable possibility that the incident, experience or outcome may have been caused by the procedures involved in such research); and
- Suggests that the research places subjects or others at a greater risk of harm (including physical, psychological, economic or social harm) than was previously known or recognized.

Adverse Event of Special Interest (AESI)

AESIs are a subset of Events to Monitor (EtMs) of scientific and medical concern specific to the product, for which ongoing monitoring and rapid communication to the Principal Investigator is required. Such an event might require further investigation in order to characterize and understand it. Depending on the nature of the event, rapid communication by the Principal Investigator to other parties (e.g., Regulatory Authorities) may also be warranted.

**Columbia University Irving Medical Center
Herbert Irving Comprehensive Cancer Center
CUMC IRB – AAAT0174**

The following AEs are considered of special interest and must be reported to the Principal Investigator expeditiously, irrespective of regulatory seriousness criteria:

The following confirmed treatment-emergent autoimmune conditions:

- Systemic lupus erythematosus
-

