- Nephritis
- Ocular toxicities (e.g., uveitis, retinitis, optic neuritis)
- Grade \geq 2 cardiac disorders (e.g., atrial fibrillation, myocarditis, pericarditis)
- Vasculitis
- Autoimmune hemolytic anemia.
- Severe cutaneous reactions (e.g., Stevens-Johnson syndrome, dermatitis bullous, toxic epidermal necrolysis)
- Events suggestive of hypersensitivity, cytokine release syndrome, infusion-related reactions, macrophage activating syndrome, hemophagocytic lymphohistiocytosis
- Cases of potential drug--induced liver injury that include an elevated ALT or AST in combination with either an elevated bilirubin or clinical jaundice, as defined by Hy's law
 - Treatment-emergent ALT or AST \geq 3x ULN in combination with total bilirubin \geq 2x ULN
 - Treatment-emergent ALT or AST \geq 3x ULN in combination with clinical jaundice
- Data related to a suspected transmission of an infectious agent by the study drug (STIAMP), as defined below:

Any organism, virus, or infectious particle (e.g., prion protein transmitting transmissible spongiform encephalopathy), pathogenic or non-pathogenic, is considered an infectious agent. A transmission of an infectious agent may be suspected from clinical symptoms or laboratory findings that indicate an infection in a patient exposed to a medicinal product. This term applies only when a contamination of the study drug is suspected.

Adverse Event Reporting Period

The study period during which AEs and SAEs where the patient has been exposed to Genentech product must be reported during the reporting period which begins after informed consent is obtained. Subjects will be followed for serious adverse events and adverse events of special interest for 90 days after their last dose of study drug or initiation of new anti-cancer therapy, whichever occurs first. For all other adverse events, Subjects will be followed for 30 days after their last dose of study drug or initiation of new anti-cancer therapy, whichever occurs first. Investigators are instructed to report all SAEs and AESIs considered related to study treatment regardless of time after study.

Post-study Adverse Event

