10.3 Recording of Adverse Events

At each contact with the subject, the treating investigator must seek information on adverse events by specific questioning and, as appropriate, by examination. Information on all adverse events should be recorded immediately in the source document, and also in the appropriate adverse event module of the case report form (CRF). All clearly related signs, symptoms, and abnormal diagnostic procedures results should be recorded in the source document, though should be grouped under one diagnosis.

All adverse events occurring during the study period must be recorded. The clinical course of each event should be followed until resolution, stabilization, or until it has been determined that the study treatment or participation is not the cause. Serious adverse events that are still ongoing at the end of the study period must be followed up to determine the final outcome. Any serious adverse event that occurs after the study period and is considered to be possibly related to the study treatment or study participation should be recorded and reported immediately.

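### The 90-day follow-up for serious and special-interest adverse events has no marked assessment after the discontinuation visit; patients who stop for progression and start no new therapy have only a survival check that may be done from records alone.

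*Combined protocol and SAP*

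**What the plan says.** **The duty.** Section 10.2 states: "Subjects will be followed for serious adverse events and adverse events of special interest for 90 days after their last dose of study drug". The window closes earlier if new anti-cancer therapy starts. Note 4 of the calendar repeats this. SAEs and AESIs, whether or not they are thought related to treatment, "will be reported until 90 days after the last dose of study drug or initiation of new anti-cancer therapy, whichever occurs first". Section 10.2 also says that AESIs "must be reported to the Principal Investigator expeditiously, irrespective of regulatory seriousness criteria", so an AESI need not involve a hospital admission to count.

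**The schedule.** In the Section 12 grid the Adverse Events row is marked from Cycle 2 Day 1 through maintenance and at the Treatment Discontinuation Visit, timed "<30 days after last dose". The Survival Follow up column has marks only for survival status and for a CT scan. Note 12 restricts that scan, opening with "If the patient discontinued study treatment for any reason other than disease progression".

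**The survival check.** The column header gives a three-monthly interval without a starting point. Note 5 says: "Survival visits are to occur every 4 to 6 months from the date of the 6 month Follow-up visit". The grid has no such six-month visit. Note 5 adds: "Survival follow-up information will be collected via telephone calls, patient medical records, and/or clinic visits".

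**The concern.** A site can complete every scheduled item in the calendar for a patient who stops for progression and still make no patient contact between the discontinuation visit and day 90. If the survival check is then done from the chart, nobody asks the patient about new events. Hospital admissions and deaths will usually appear in records. An AESI managed elsewhere without admission may not, and neither may an SAE that the patient and the treating physician think unrelated to the study.

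Safety of adding liver-directed SBRT is a secondary objective (Section 2). In a trial of 18 patients, incomplete ascertainment after treatment would make the safety tabulation look slightly cleaner than it should.

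**Working it through.** The plan states no figure on this point, so there is nothing to reproduce. The check sets the duty against the schedule and counts days.

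**1. Which patients have a scheduled contact after the discontinuation visit?**
- Stopped without progression: scans continue every 6 weeks in the first 12 months and every 9 weeks after that (Section 5.2, note 12). In the first year, attendances fall inside the window.
- Stopped for progression, new therapy started: the window closes when that therapy starts.
- Stopped for progression, no new therapy: scans end at progression, or when treatment stops for those treated beyond it (note 11). Section 8.5 sets two years of follow-up but no visits. Only the survival check remains.

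**2. How long is the part of the window with no marked assessment?** Let V be the day of the discontinuation visit and T the day new therapy starts, both counted from the last dose. The unmarked length is min(90, T) − V, or zero if T is no later than V. With no new therapy by day 90:
- V = 29 (the latest day allowed): 90 − 29 = 61 days
- V = 21 (assumed): 90 − 21 = 69 days
- V = 0 (the extreme): 90 − 0 = 90 days

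**3. When does the first survival check fall?** One month is 365.25/12 = 30.44 days.
- Header, counted from the last dose: 3 × 30.44 = day 91
- Header, counted from a visit on day 21: 21 + 91 = day 112
- Header, counted from a visit on day 29: 29 + 91 = day 120, which is 120 − 90 = 30 days after the window closes
- The unlisted six-month visit in note 5, if counted from the last dose: 6 × 30.44 = day 183

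None of these readings puts a scheduled contact between day 30 and day 90.

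**4. Do other provisions supply the contact?**
- Section 10.3: "At each contact with the subject, the treating investigator must seek information on adverse events by specific questioning". This applies fully to a call or visit, but a chart review is not a contact with the subject.
- Section 10.2, post-study events: patients are told to report later events thought related to participation, and ongoing treatment-related events are followed. Unrelated new events fall outside both.
- Section 8.5: follow-up to resolution covers adverse events that led to removal.
- Section 10.4.2: covers deaths in the reporting period.
- Section 18.8: the 24-hour clock starts when the site learns of the event.
- Sections 14.4 and 18.7: monitors check against source documents, so they see what the site's records hold.

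Each provision lowers the risk. None schedules a patient contact for new events of any cause between the discontinuation visit and day 90.

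**The case against.** The best defence is that the duty is stated twice and is active, and that nothing makes the grid a complete list of occasions for collecting adverse events. The same row has no mark at Cycle 1 Day 1, although reporting begins after consent and Section 10.3 requires questioning at every contact. This stands. A reader might infer from the blank survival cell that SAEs and AESIs after day 30 are not to be collected, and the documents do not support that.

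Second, the natural reading of the header puts the first survival check at about day 91, just as the window closes. If that check is a call or a visit, Section 10.3 applies and earlier events can be recovered. This also stands, and it is why the point is small. It does not cover a records-only check, which note 5 permits.

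Third, the patients in whom toxicity is already known are better covered. Those who stop for toxicity without progression keep their scans, and events that caused removal are followed to resolution or stabilization. Deaths are reported whatever their cause, and related SAEs and AESIs are reportable at any time. The residue is narrow: mainly unrelated SAEs and non-hospitalized AESIs that are not in the site's records.

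Finally, a reader might take note 5 alone and infer that the first survival check comes 10 to 12 months after the last dose (day 304 to 365). That ignores the three-monthly header and assumes a starting date for the six-month visit. The two texts can be reconciled as three-monthly to month 6 and every 4 to 6 months after that. The fair criticism is only that the plan does not say so.

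**Conclusion.** The point holds as a minor defect in the calendar. The plan has the reporting duty but no scheduled contact to carry it out in patients who stop for progression and start no new therapy. In that group at least about 60 days of the 90-day window have no marked adverse-event assessment, and more if the discontinuation visit is early. The figure assumes that no new therapy starts by day 90. It measures time without a marked assessment and is not a share of events lost.

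The number of events missed cannot be derived from the documents. A reader might treat one patient in 18 (1/18 = 5.6 percentage points) as the expected loss. It shows only how much a single event weighs in this sample. The primary endpoint, 6-month progression-free survival, and its rule of at least 6 of 16 patients are unaffected.

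**What to change.** Amend the Section 12 calendar:

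1. Make the first survival follow-up a direct contact by telephone or clinic visit at day 90 (+7) after the last dose. Allow records only if the patient has died or cannot be reached, and document that.
2. Mark Adverse Events at this contact. It should cover SAEs and AESIs of any cause since the discontinuation visit, up to day 90 or the start of new anti-cancer therapy if earlier.
3. Count the three-monthly interval from the last dose and bring note 5 into line with the header, either by defining the six-month visit or by removing the reference to it. The later survival interval can be left to the sponsor, because closing this gap does not need three-monthly contacts throughout.

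The cost is a calendar amendment, at most 18 short calls (one per patient), and slightly more events to report. Sample size and analysis do not change.

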13 MEASUREMENT OF EFFECT

13.1 Antitumor Effect – Solid Tumors

For the purposes of this study, patients will undergo a baseline scan during screening and should be re-evaluated for response every 6 weeks for 12 months beginning within -7d of Cycle 4, Day 1 and thereafter every 9 weeks.

Response and progression will be evaluated in this study using the international criteria proposed by the revised Response Evaluation Criteria in Solid Tumors (RECIST) guideline (version 1.1)⁵³. Changes in the largest diameter (unidimensional measurement) of the tumor lesions and the shortest diameter in the case of malignant lymph nodes are used in the RECIST criteria.

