5.2 Intervention

All patients must undergo a mandatory biopsy of a liver lesion prior to chemotherapy initiation. Cycle 1 of chemoimmunotherapy will be administered as per standard of care, with radiation planning to be done subsequently in anticipation of liver-directed SBRT (3 doses of 10 Gy administered on alternating days to up to three liver lesions, measuring no greater than 5 cm each) to be given within +/-3 days of cycle 2.

Subjects will continue to receive study treatment (four 21-day cycles of induction chemoimmunotherapy followed by maintenance atezolizumab every 3 weeks) until disease progression or intolerance of treatment. During the maintenance phase, prophylactic cranial irradiation is permitted; consolidative thoracic radiation may be considered if deemed clinically appropriate by the treating investigator in discussion with the principal investigator.

If clinically feasible, it is recommended that the patient undergo a tumor biopsy sample collection at the time of radiographic disease progression. These data will be used to explore whether radiographic findings are consistent with the presence of a tumor. Additionally, these data will be analyzed to evaluate the association between changes in tumor tissue and clinical outcome and to further understand the potential mechanisms of progression and resistance to study treatment. This exploratory biomarker evaluation will not be used for any treatment-related decisions.

Patients will undergo tumor assessments prior to radiation administration and every 6 weeks (\pm 7 days) for the first 12 months following Cycle 1, Day 1, regardless of treatment dose delays. After 12 months, tumor assessments will be required every 9 weeks (\pm 7 days). Patients will undergo tumor assessments until radiographic disease progression per RECIST v1.1, withdrawal of consent, study termination by the principal investigator, or death, whichever occurs first.

Patients who continue treatment beyond radiographic disease progression per RECIST v1.1 will continue to undergo tumor assessments every 6 weeks (\pm 7 days), or sooner if symptomatic deterioration occurs. For these patients, tumor assessments should continue every 6 weeks (\pm 7 days), regardless of time in the study, until study treatment is discontinued.

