Patients who discontinue treatment for reasons other than radiographic disease progression (e.g., toxicity) will continue scheduled tumor assessments at the same frequency as would have been followed if the patient had remained on study treatment (i.e., every 6 weeks [\pm 7 days] for the first 12 months following Cycle 1, Day 1 and then every 9 weeks [\pm 7 days] thereafter, regardless of treatment dose delays) until radiographic disease progression per RECIST v1.1, withdrawal of consent, study termination by the principal investigator, or death, whichever occurs first, regardless of whether patients start a new anti-cancer therapy.

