9.3.1 Hematologic toxicity

At the start of each cycle, the ANC should be $\geq 1500/\text{mm}^3$ and the platelet count should be $\geq 100,000/\text{mm}^3$. Treatment should be delayed for up to 42 days to allow sufficient time for recovery. If the counts have not recovered in 3 weeks, the patient's carboplatin may be dose-reduced, held until adequate neutrophil recovery, or discontinued, according to physician judgment and local standard practice. Growth factors may be used in accordance with American Society of Clinical Oncology (ASCO) and the 2015 NCCN guidelines⁵². Upon recovery, dose adjustments at the start of a subsequent cycle may be made on the basis of the lowest platelet and neutrophil values from the previous cycle (see Table 1).

Table. 1 Carboplatin Dose Modification for Hematologic Toxicities

Toxicity^a	Carboplatin
ANC $< 500/\text{mm}^3$ and platelets $\geq 50,000/\text{mm}^3$	75% of previous dose
Platelets $< 25,000/\text{mm}^3$, regardless of ANC	75% of previous dose
Platelets $< 50,000/\text{mm}^3$, with grade ≥ 2 bleeding regardless of ANC	75% of previous dose
ANC $< 1000/\text{mm}^3$ plus fever of $\geq 38.5^\circ\text{C}$	75% of previous dose

^aNadir prior to cycle

Dose reductions for the first episode of neutropenic fever or thrombocytopenia (platelet count $< 25,000$ or $< 50,000$ with bleeding or that requires transfusion) should be considered permanent.

If a second episode of neutropenic fever or thrombocytopenia requiring dose reduction occurs, the dose of carboplatin should be reduced according to physician judgment and local standard practice. Colony-stimulating factors, such as granulocyte colony-stimulating factor, may be used instead of dose reduction for neutropenic fever or Grade 4 neutropenia according to the local standard practice and ASCO guideline. Patients who require a third dose reduction should be considered for permanent discontinuation of carboplatin.

In the event that dose adjustments are needed for both ANC and platelets, patients should receive the lower dose.

Investigators should be vigilant and alert to early and overt signs of myelosuppression, infection, or febrile neutropenia so that these complications can be promptly and appropriately managed. Patients should be made aware of these signs and encouraged to seek medical attention at the earliest opportunity.

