11.2 Treatment Regimen

Induction phase- four cycles of 21 days duration each will be administered as follows:

- Atezolizumab fixed dose of 1200 mg administered IV on day 1
- Carboplatin AUC=5 administered IV on day 1
- Etoposide 100 mg/m² on days 1, 2, and 3 of each cycle
- Stereotactic body radiation therapy administered to up to 3 liver lesions within +/-3 days of cycle 2 day 1.

Maintenance phase: atezolizumab 1200 mg administered on day 1 in 21 day cycles until withdrawal criteria are met as outlined in [**Section 5.5**](#).

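### Tumor assessments run on two incompatible clocks (C1D1 in Section 5.2 and calendar footnote 11, C4D1 in Section 13.1), and no scan is named as deciding 6-month PFS

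*Combined protocol and SAP*

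**What the plan says.** - **Section 5.2, interval:** "Patients will undergo tumor assessments prior to radiation administration and every 6 weeks". A tolerance of one week either side is allowed.
- **Section 5.2, clock:** this interval applies "for the first 12 months following Cycle 1, Day 1, regardless of treatment dose delays". For patients who stop treatment without progression it repeats the rule: "for the first 12 months following Cycle 1, Day 1 and then every 9 weeks".
- **Section 12, footnote 11:** the same interval, "approximately every two cycles) for 12 months following Cycle 1, Day 1", again regardless of delays.
- **Section 13.1:** after the baseline scan, patients "should be re-evaluated for response every 6 weeks for 12 months beginning within -7d of Cycle 4, Day 1".
- **Section 12, grid:** as the table reads in the available text, the row "CT chest and abdomen w/ contrast" is marked at screening, then not again until C4D1. Its maintenance cell carries the marker for footnote 11.
- **Section 9.3.1:** C4D1 can move. "Treatment should be delayed for up to 42 days to allow sufficient time for recovery"
- **Sections 13.7 and 15.1:** PFS6 is the proportion alive and progression-free 6 months after treatment start. No day count, scan or window is given. At least 6 of 16 is a positive result.
- **Section 15.2:** the primary analysis takes patients with an evaluable 6-month outcome, a term it does not define.

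**The concern.** Both rules are operative and a site cannot follow both. Radiographic progression is dated at the scan that shows it, so the timing of the last scan before the landmark helps decide who counts as progression-free. A progression arising between days 147 and 168 is seen at week 24 on the C1D1 clock and counts as a failure. On the C4D1 clock it may not be seen until week 27, after the landmark, and the patient counts as a success. With a threshold of 6 of 16, one patient can settle the result. The trial projects three centers, which may read the schedule differently. Without a rule on which scan informs 6-month status, that choice could be made after the data are known.

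**Working it through.** **The plan's own design.** With n = 16, a threshold of 6, and rates of 0.20 and 0.45 (Section 15.1), the exact binomial gives P(X ≥ 6 | 0.20) = 0.0817 and P(X ≥ 6 | 0.45) = 0.8024. The design reproduces.

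**Scan dates.** Days are counted after C1D1. Cycles last 21 days, so C4D1 is day 63 without delay. The plan gives no day count for 6 months; I assume 182.6 days.

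| | Section 5.2 / footnote 11 | Section 13.1, no delay |
|---|---|---|
| Formula | 42k, k = 1, 2, … | 63 + 42k, k = 0, 1, … |
| Nominal days | 42, 84, 126, 168, 210 | 63, 105, 147, 189 |
| First-scan window | 35-49 | 56-63 |
| Last nominal scan before 6 months | day 168 (week 24) | day 147 (week 21) |

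The last row is the same for any definition of 6 months from 168 to 184 days.

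**Delay.** If C4D1 slips by d days, Section 13.1 gives 63 + d + 42k. For d = 0, 7, 14, 21, 28, 35 and 42, the last nominal look before 6 months is day 147, 154, 161, 168, 175, 182 and 147. On the C1D1 clock it stays at day 168.

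**Illustration of size.** Assume exponential PFS, S(t) = p^(t/182.6), nominal scans, no delays, and every event first seen on a scan.

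| True PFS6 | S(147) | S(168) | P(≥6 of 16), day 147 | P(≥6 of 16), day 168 | Difference |
|---|---|---|---|---|---|
| 0.20 | 0.2737 | 0.2275 | 0.2569 | 0.1348 | 0.122 |
| 0.45 | 0.5258 | 0.4797 | 0.9281 | 0.8620 | 0.066 |

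- Patients classified differently: 16 × 0.0463 = 0.74 at 20%, and 16 × 0.0461 = 0.74 at 45%.
- A patient clear at day 168 was also clear at day 147. The classifications are therefore nested, and the differences are the shares of trials whose decision changes when the whole trial uses one clock rather than the other.
- If 5 of 16 patients follow Section 13.1 (about one center of three, assuming equal accrual) and 11 follow Section 5.2, P(≥6 of 16) is 0.169 at 20% against 0.135 with all 16 on Section 5.2, about 3.4 points. At 45% it is 0.886 against 0.862, about 2.4 points.

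**Sensitivity (whole-trial contrast, at 20% and 45%).**
- Halving the gap between each scan-based rate and the true rate, an arbitrary allowance for exactly dated deaths: 5.0% and 4.2%.
- Weibull S(t) = p^((t/182.6)^k), k = 0.8: 9.0% and 5.9%.
- Weibull, k = 1.5: 21.5% and 7.4%.
- The exponential through 20% at 6 months has median 6 × ln 2 / ln 5 = 2.6 months. Section 3 gives 4.3 months for atezolizumab-treated patients with liver metastases. Fitting both needs k = ln(ln 5 / ln 2) / ln(6 / 4.3) ≈ 2.5, and the difference at 20% is then about 40 points.

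**The case against.** The strongest reply is that Section 13.1 is a lone outlier. Section 5.1 sends the reader to Section 12 for the schedule, and footnote 11 there agrees with Section 5.2. That stands, and it shows which text to change. It does not remove the conflict, because Section 13.1 is the operative section on measuring progression and the grid's first on-treatment mark is also at C4D1.

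A reader might infer several stronger points that the documents do not support:

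- **That the calendar grid also fixes week 21.** Its maintenance cell carries footnote 11, so the grid can be read as C4D1 followed by weeks 12, 18 and 24. Week 21 rests on Section 13.1 alone.
- **That the grid omits a required pre-radiation scan.** Section 11.2 has "Stereotactic body radiation therapy administered to up to 3 liver lesions within +/-3 days of cycle 2 day 1", but Section 5.2 does not say that the assessment before radiation must follow screening. The screening CT could satisfy it.
- **That type I error is inflated to 13.5% or 25.7%.** The documents do not give the scan schedule behind the historical 20%, which may carry the same lag.
- **That the sample size is wrong.** It reproduces.

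Two other readings narrow the gap. Counting Section 5.2 from a scan at about week 3 gives the same nominal weeks as Section 13.1, but Section 5.2 names C1D1 as its origin. If a first Section 13.1 scan 7 days early carries forward, the fourth falls on day 182. However, Section 13.1 gives that tolerance only for the start.

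**Conclusion.** The inconsistency is real and should be fixed. Confidence is high on the conflict over anchor and delays, and on week 24 against week 21 as the plain readings. It is low on the size. The 12.2% and 6.6% are contrasts between whole trials on one clock or the other; mixed practice across centers, the likelier route to harm, gives about 3.4 and 2.4 points under the same assumptions. All these figures assume exponential PFS, nominal scans without delay, and every event found on a scan. Exactly dated deaths would shrink them, and a curve with rising hazard would enlarge them. The case for the change rests on the contradictory text and the missing rule for 6-month status, not on any one of these percentages.

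**What to change.** 1. Change Section 13.1 and the Section 12 CT row to match Section 5.2 and footnote 11: every 6 weeks from C1D1, independent of delays. State whether the pre-radiation assessment is a separate scan or is met by the screening scan.
2. Give 6 months a day count and schedule one assessment there, for example by moving the week-24 scan to about week 26 (day 182). Name it, with its window, as the scan that informs 6-month status, and state when the series resumes.
3. In Sections 13.7 and 15.1, state that progression on or before that scan, or death by 6 months, is a failure.
4. In Section 15.2, state that every patient who progresses or dies earlier is evaluable and counted as a failure, even without a 6-month scan. Scheduled scans stop at progression, so defining evaluability by that scan alone could drop early failures.

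**Cost.** Wording and calendar edits, and one 8-week gap (weeks 18 to 26). There are four scans by 6 months, against three on the nominal Section 13.1 schedule. In the same exponential illustration, a day-182 scan gives S = 0.2011 and 0.4512, so the chance of at least 6 of 16 is 8.4% at true PFS6 20% and 80.5% at 45%. The design values are 8.2% and 80.2%. Letting a week-27 scan decide is less attractive: it falls after the landmark and gives 6.5% and 77%.
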